#### **6.5.2 Corticosteroids**

Subjects entering the study while taking oral corticosteroids cannot exceed the dose of 5 mg of prednisone or equivalent daily. The investigator may prescribe corticosteroids at a regularly scheduled visit or Disease Assessment visit ([Section 7.2.7](#)) if the subject is experiencing increased disease activity. However, any increase in dose or treatment with corticosteroids for increased disease activity must not exceed 2-weeks.

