#### **6.5.1 Analgesics and NSAIDs**

If the study subject enters the study taking acetaminophen, narcotic analgesics, or NSAIDs on a scheduled basis or as needed, the dose can be reduced or discontinued during the study if necessary for safety reasons or standard of care.

If the study subject is not taking acetaminophen, narcotic analgesics, or NSAIDs prior to entering the study and they take any of these agents for reasons related to RA, they may take these agents but must be seen at a regularly scheduled visit or a Disease Assessment visit ([Section 7.2.7](#)) no later than 1 week after commencing treatment. Analgesics and NSAIDs should not be taken for more than 2 weeks at a time.

If at any time the subject is taking acetaminophen, narcotic analgesics or NSAIDs these must not be used within 12 hours before a scheduled study visit, with the exception of oxycontin which may not be used within 24 hours of a scheduled study visit.

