## **6.8 Excluded Treatments and/or Procedures During Study Period**

Proscribed medications during this study include the following:

- Anakinra
- Abatacept
- Any other investigational agents or commercially available biologics
- Azathioprine
- Leflunomide
- Cyclosporine
- Cytotoxic agents including chlorambucil, cyclophosphamide, nitrogen mustard, or other alkylating agents
- Gold
- Intraarticular, intramuscular, or intravenous corticosteroids, including adrenocorticotrophic hormone
- Intraarticular hyaluronic acid injections
- Mycophenolate mofetil
- ProSORBA Column
- Systemic tacrolimus
- Live vaccines

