### **7.2.7 Disease Assessment Visit**

Subjects can be seen at a regularly scheduled visit or at a disease assessment visit any time after screening to assess disease activity to either:

- establish Part 2 eligibility criteria during the run-in period OR
- to determine if subject can receive rescue treatment after randomization

During the double-blind randomized treatment period, if the subject meets the criteria for disease worsening as defined in [Section 3.1.2](#) subjects will initiate treatment with etanercept and methotrexate at the same dose they were receiving during the run-in period. Subjects will continue to receive etanercept plus methotrexate for the remaining study visits per [Table 1](#).

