4.1 Study Endpoints

4.1.1 Primary Endpoint

- SDAI remission (≤ 3.3) at week 48

The primary estimand consists of:

- Target population – patients with a history of moderate to severe rheumatoid arthritis (RA) who are on etanercept and methotrexate combination therapy and who are in very good disease control.
- Endpoint – SDAI remission (SDAI \leq 3.3) at week 48
- Intercurrent events – there are 2 intercurrent events: first, discontinuation of IP before week 48; second, disease-worsening after randomization which triggers initiation of rescue therapy. Treatment effects will be estimated for subjects regardless of whether subjects complete 48 weeks of IP.
- Summary measure – difference in the proportion of subjects achieving SDAI \leq 3.3 (yes/no) at Week 48 on etanercept monotherapy and that of subjects achieving SDAI \leq 3.3 (yes/no) at Week 48 on methotrexate monotherapy.

In summary, the primary estimand is the difference in proportions of subjects in etanercept monotherapy and methotrexate monotherapy maintaining SDAI remission at Week 48 without experiencing disease-worsening on study in adults with a history of moderate to severe RA who have been on etanercept and methotrexate combination therapy and in very good RA disease control, regardless of adherence to treatment and completion of 48 weeks of IP.

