The swollen joint count is an assessment of the swelling of joints using 0-1 point scale (0=none, 1=present). Joints that are marked as permanently inevaluable due to being replaced or fused are not counted as swollen for that specific visit. Joints that are marked with an intra-articular corticosteroid injection are considered swollen for that specific visit. The total swollen joint count is calculated by summing the number of joints with present swelling.

Swollen Joint Count (66)	
Temporomandibular joints (n=2)	Metacarpophalangeal joints (MCP) (n=10)
Sternoclavicular joints (n=2)	Fingers distal interphalangeal joints (DIP) (n=8)
Acromioclavicular joints (n=2)	Knees (n=2)
Shoulders (n=2)	Ankles (n=2)
Elbows (n=2)	Tarsi (n=2)
Wrists (n=2)	Metatarsal phalangeal joints (MTP) (n=10)
Fingers proximal interphalangeal joints (PIP) (n=10)	Toes proximal interphalangeal joints (PIP) (n=10)

Swollen Joint Count (28) Plus Feet and Ankles	
Shoulders (n=2)	Metacarpophalangeal joints (MCP) (n=10)
Elbows (n=2)	Proximal interphalangeal joints (Fingers PIP) (n=10)
Wrists (n=2)	Knees (n=2)
Ankles (n=2)	Tarsi (n=2)
Metatarsal phalangeal joints (MTP) (n=10)	Toes proximal interphalangeal joints (PIP) (n=10)

Swollen Joint Count (28)	
Shoulders (n=2)	Metacarpophalangeal joints (MCP) (n=10)
Elbows (n=2)	Proximal interphalangeal joints (Fingers PIP) (n=10)
Wrists (n=2)	Knees (n=2)

Tender Joint Count

The tender joint count is an assessment of the pain and/or tenderness of joints using 0-1 point scale (0=none, 1=present). Joints that are marked as permanently inevaluable due to being replaced or fused are not counted as tender for that specific visit. Joints that are marked with an intra-articular corticosteroid injection are considered tender for that specific visit. The total tender joint count is calculated by summing the number of joints with present tenderness.

Tender Joint Count (68)	
Temporomandibular joints (n=2)	Metacarpophalangeal joints (MCP) (n=10)
Sternoclavicular joints (n=2)	Metatarsal phalangeal joints (MTP) (n=10)
Acromioclavicular joints (n=2)	Toes proximal interphalangeal joints (PIP) (n=10)
Shoulders (n=2)	Knees (n=2)
Elbows (n=2)	Ankles (n=2)
Wrists (n=2)	Tarsi (n=2)
Fingers proximal interphalangeal joints (PIP) (n=10)	Hip (n=2)
Fingers distal interphalangeal joints (DIP) (n=8)	

Tender Joint Count (28) Plus Feet and Ankles	
Shoulders (n=2)	Metacarpophalangeal joints (MCP) (n=10)
Elbows (n=2)	Proximal interphalangeal joints (Fingers PIP) (n=10)

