Appendix E. Concomitant Medications

The following concomitant medications will be tabulated:

- hydroxychloroquine,
- sulfasalazine,
- minocycline,
- prednisone (5mg daily or less),
- and NSAIDs

The Prednisone dosage of 5 mg daily or less is of interest because entry criteria allows for this dosage.

Only concomitant medications with a partial or complete end date are tabulated.

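### Corticosteroid courses given for increased disease activity are permitted but ignored in the primary endpoint, its sensitivity analyses and the committed tables, so an unconfirmed flare, or one treated shortly before Week 48, can score as maintained remission

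*Protocol*

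**What the plan says.** **Permission.** Protocol 6.5.2: "The investigator may prescribe corticosteroids at a regularly scheduled visit or Disease Assessment visit" when disease activity has increased, and "any increase in dose or treatment with corticosteroids for increased disease activity must not exceed 2-weeks". Protocol 6.8 excludes other routes ("Intraarticular, intramuscular, or intravenous corticosteroids, including adrenocorticotrophic hormone"), so the permission is in effect for oral courses. Under Protocol 7.2.7, "Subjects can be seen at a regularly scheduled visit or at a disease assessment visit any time after screening". The number of courses is not limited, and no interval between a course and an SDAI assessment is stated.

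**Worsening.** Protocol 3.1.2 has three limbs: SDAI above 3.3 and up to 11 at two consecutive visits at least two weeks apart; SDAI in that range at three or more separate visits; or a single SDAI above 11.

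**Primary endpoint.** SAP 4.1.1 states that "there are 2 intercurrent events: first, discontinuation of IP before week 48; second, disease-worsening after randomization which triggers initiation of rescue therapy". SAP 6.2 scores a responder on two conditions only: Week 48 SDAI of 3.3 or less, and no disease-worsening during the study.

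**Sensitivity analyses.** SAP 11.5.1.2 has an observed-case analysis and a multiple imputation analysis. The latter imputes missing SDAI values and values after rescue.

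**Reporting.** SAP Appendix E lists the medications to be tabulated; the only corticosteroid entry is "prednisone (5mg daily or less"). SAP 11.6.5 says that a summary of all concomitant medications may be provided. Both are limited to records with a partial or complete end date.

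**Data.** Protocol 6.5 already collects dose, indication, route, and start and stop dates.

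**The concern.** The endpoint is meant to show whether remission is maintained on the randomized treatment. A steroid course given because disease activity has risen is additional treatment for the condition being measured. If the SDAI that decides the outcome is taken under its effect, the response is partly due to the steroid.

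Elsewhere the plan does guard against treatment affecting an assessment. For analgesics and NSAIDs, "these must not be used within 12 hours before a scheduled study visit" (Protocol 6.5.1). In SAP Appendix A, "Joints that are marked with an intra-articular corticosteroid injection are considered swollen for that specific visit", with a matching rule for tenderness. Permitted systemic courses have no counterpart.

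At stake is the reading of the primary difference and of time to disease-worsening. If steroid use differs by arm, the comparison mixes the randomized treatments with the added steroid, and no committed output would show a reader how often this happened.

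**Working it through.** **1. Which flares can be masked.** A course has to be prescribed at a visit where the Schedule of Assessments includes the SDAI components.

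- SDAI above 11 at that visit: already worsening, hence non-response. Not maskable.
- SDAI above 3.3 and up to 11 for the third time at separate visits: already worsening, whatever was measured in between. Not maskable.
- SDAI above 3.3 and up to 11 for the first or second time, without a consecutive confirming visit: maskable.

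**2. Two routes under the rules as written.**

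- *Broken sequence.* SDAI is 8 at a visit and a 2-week course is given. A Disease Assessment visit on day 14 of the course shows SDAI of 3.3 or less. The two-consecutive-visit limb is not met.
- *Week 48.* SDAI is 8 at a Disease Assessment visit on Study Day 325 and a course is started; SDAI is 3 on Day 337. SAP Appendix A selects the value closest to Day 337, which is the on-steroid one. Without earlier worsening, a value in this range at the preceding visit two or more weeks before, or two earlier values in it, SAP 6.2 scores 1.

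**3. Whether another analysis catches it.** Observed-case keeps the on-steroid SDAI. Multiple imputation removes values only after rescue, so it keeps it too. The optional analysis in SAP 10.4 excludes subjects with major protocol deviations, and permitted steroid use is not a deviation.

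**4. The plan's own figures.** Inputs (Protocol 10.2): 72% v 50%, two-sided 5%, 100 per arm, 90% power.

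Power = Φ{[d − 1.96·√(2p̄(1−p̄)/n)] / √([p₁(1−p₁)+p₂(1−p₂)]/n)}

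With p̄ = 0.61 and n = 100: (0.22 − 1.96 × 0.0690) / 0.0672 = 1.262, so power = 89.7%. The required n is 102 per arm with pooled variance and 99 unpooled, and 250/0.70 rounds up to 358 enrolled. The stated figures reproduce.

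**5. Illustrative effect of masking.** No steroid rate is given, so the masked fraction m of true non-responders is an assumption. With equal m in both arms, p₁ = 0.72 + 0.28m, p₂ = 0.50 + 0.50m, and d = 0.22(1 − m).

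| m, both arms | Etanercept | Methotrexate | Difference (points) | Power |
|---|---|---|---|---|
| 0 | 72.0% | 50.0% | 22.0 | 89.7% |
| 5% | 73.4% | 52.5% | 20.9 | 87.0% |
| 10% | 74.8% | 55.0% | 19.8 | 84.0% |
| 20% | 77.6% | 60.0% | 17.6 | 77.0% |

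Masking of 5% to 20% in the methotrexate arm only: difference 19.5 to 12.0 points, power 81.7% to 43.2%. In the etanercept arm only: difference inflated to between 23.4 and 27.6 points.

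**6. What the proposed analysis could show.** Reclassify a fraction s of scored responders as non-responders, starting from 72% v 50%. With s = 5%, 10% or 20% in both arms, rates are 68.4/47.5%, 64.8/45.0% or 57.6/40.0%, and power in that analysis is 85.5%, 80.8% or 70.5%. With s = 5% on etanercept and 10% to 20% on methotrexate, power is 92.2% to 98.5%.

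**The case against.** The strongest reply is that the opening is narrow. Scheduled visits are 12 weeks apart. Without an extra Disease Assessment visit, the SDAI after a 2-week course falls about 10 weeks after it ends. Both routes need such an extra visit at a particular time, no two-week confirmatory visit is required, and the documents do not say how long suppression lasts. The separate-visits limb also limits repeated masking. This stands: it bounds how often masking can occur, but does not close the gap.

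Four stronger readings are tempting and are not supported.

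- *That steroids are allowed at any time and can hide any flare.* They must be prescribed at a scheduled or Disease Assessment visit, and an SDAI above 11 there already counts as worsening.
- *That the SAP leaves steroids out of its tables.* It commits to prednisone at 5 mg daily or less and allows an any-dose summary. What is missing is a commitment to show courses above 5 mg, or courses given for disease activity.
- *That the documents contradict themselves on masking.* Different rules for different drug classes are not a contradiction, and the joint-injection rule scores a route that the protocol excludes.
- *That the bias must run toward no difference because the arm that flares more gets more steroid.* That is plausible, but no figure in the documents supports it.

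**Conclusion.** The gap is real on the current text: permitted steroid courses for increased disease activity have no stated handling in the estimand, the responder rule, either sensitivity analysis or any committed table. Its reach is limited to unconfirmed flares with SDAI above 3.3 and up to 11, and to flares treated shortly before Week 48.

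The size and direction of any bias cannot be known from the documents. Equal masking in both arms, assumed at 5% to 20% of non-responders, costs 1.1 to 4.4 points of difference (22.0 − 20.9 and 22.0 − 17.6) and 2.7 to 12.7 points of power (89.7 − 87.0 and 89.7 − 77.0). Unequal masking could move the estimate either way. The stated sample size is not in error. This is an inexpensive improvement to how the primary result can be interpreted, not a flaw that invalidates it.

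**What to change.** SAP only.

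1. **Section 11.5.1.2.** Add a sensitivity analysis of the primary endpoint, pre-specified before unblinding. A subject is a non-responder if a corticosteroid was started or increased for RA activity and was in use within a stated window before the Week 48 SDAI. In the same analysis, an SDAI of 3.3 or less measured on such a course does not break the consecutive-visit worsening sequence. The sponsor should justify the window and vary it.
2. **Appendix E.** Commit to a by-arm table of all post-randomization corticosteroid starts and increases at any dose, including ongoing records without an end date, with the number of subjects on such a course at Week 48.

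The cost is one analysis and one table from data already collected. Response rates will be lower in that analysis, and power may be lower there, as step 6 of the working shows; the primary analysis is unchanged. No change to the steroid permission, rescue or any other clinical rule is proposed.

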#### **6.5.3 DMARDS**

Subjects taking sulfasalazine (not to exceed 3 g/day) and/or hydroxychloroquine (not to exceed 400 mg/day) must remain on a stable dose throughout the study.

#### **6.6 Medical Devices**

Medical devices (eg, alcohol prep pads), that are commercially available are not usually provided or reimbursed by Amgen (except, for example, if required by local regulation). The investigator will be responsible for obtaining supplies of these devices.

#### **6.7 Product Complaints**

A product complaint is any written, electronic, or oral communication that alleges deficiencies related to the identity, quality, durability, reliability, safety, effectiveness, or performance of any investigational or non-investigational product(s) or device(s).

Any product complaint(s) associated with an investigational product(s) or non-investigational product(s) or device(s) supplied by Amgen are to be reported according to the instructions provided in the IPIM.

## **6.8 Excluded Treatments and/or Procedures During Study Period**

Proscribed medications during this study include the following:

- Anakinra
- Abatacept
- Any other investigational agents or commercially available biologics
- Azathioprine
- Leflunomide
- Cyclosporine
- Cytotoxic agents including chlorambucil, cyclophosphamide, nitrogen mustard, or other alkylating agents
- Gold
- Intraarticular, intramuscular, or intravenous corticosteroids, including adrenocorticotrophic hormone
- Intraarticular hyaluronic acid injections
- Mycophenolate mofetil
- ProSORBA Column
- Systemic tacrolimus
- Live vaccines

## **6.9 Contraceptive Requirements**

### **Female Subjects**

Female subjects of child-bearing potential must agree to practice true sexual abstinence (refrain from heterosexual intercourse) or use a highly effective method of contraception during treatment and for an additional 6 months after the last dose of protocol required therapies.

Contraceptive methods that achieve a failure rate less of less than 1% per year when used consistently and correctly are considered highly effective and may include: hormonal (combined estrogen and progestogen or progestogen only), contraception associated with inhibition of ovulation (oral, injectable, implantable, intravaginal, or transdermal route), intrauterine device, intrauterine hormonal-releasing system, bilateral tubal occlusion, vasectomized partner (provided that partner is the sole sexual partner of the female participant and the vasectomized partner has received medical assessment of the surgical success), true sexual abstinence when this is in line with the preferred

and usual lifestyle of the subject. The reliability of sexual abstinence must be evaluated by the investigator and be the preferred and usual lifestyle of the subject.

If a female subject is suspected of being pregnant, the protocol-required therapies must be stopped immediately and may not be resumed until absence of pregnancy has been medically confirmed.

Females not of child-bearing potential are defined as: any female who has had a hysterectomy, OR bilateral salpingectomy, OR bilateral oophorectomy, OR are postmenopausal. Postmenopausal women are those who have had no spontaneous menses for at least 2 years.

### **Male Subjects**

Male subjects who have had a vasectomy and received medical assessment of surgical success or whose female partner has had a bilateral tubal occlusion are not required to use additional forms of contraception.

Otherwise, male subjects with a partner of child-bearing potential must agree to practice true sexual abstinence (refrain from heterosexual intercourse) or use a condom with spermicide (if spermicide is commercially available) during treatment and for an additional 6 months after the last dose of protocol required therapies. The reliability of sexual abstinence must be evaluated by the investigator and be the preferred and usual lifestyle of the subject.

The female partner should also consider using an acceptable method of effective contraction such as: hormonal, intrauterine device, intrauterine hormonal-releasing system, female barrier method (diaphragm, cervical cap, contraceptive sponge; a female condom is not an option because there is a risk of tearing when both partners use a condom).

Male subjects with a pregnant partner must practice sexual abstinence or wear a condom to prevent exposure of the unborn child to methotrexate through semen.

Unacceptable methods of birth control for male and female subjects include birth control methods that are considered unacceptable in clinical trials and include: periodic abstinence (calendar, symptothermal, postovulation methods), withdrawal (coitus interruptus), spermicides only, and lactational amenorrhoea method.

## 7. STUDY PROCEDURES

Screening assessments and study procedures outlined in this section and in [Table 1](#) can only be performed after obtaining informed consent. This includes any discontinuation of the subject's medication for the purpose of participation in this study.

All on-study visits during the run-in period should be scheduled from run-in visit 1. All on-study visits during the treatment period should be scheduled from day 1 (date of the first dose of investigational product) on the study. It is very important to attempt to perform study procedures and obtain samples at the precise timepoints stipulated below. When it is not possible to perform the study visit at the exact timepoint, the visit may be performed within the acceptable visit window as defined in the visit-specific section below.

With the exception of the screening and re-screen visits, all study procedures for a visit should be completed on the same day. Any missed visits, tests not done, or examinations that are not conducted must be reported as such on the eCRFs.

Subsequent study visits should resume on the original schedule. Missed assessments at prior visits should not be duplicated at subsequent visits.

Any blood sample collected according to the Schedule of Assessments ([Table 1](#)) may be analyzed for any of the tests outlined in the protocol and for any tests necessary to ensure subject safety. This includes testing to ensure analytical methods produce reliable and valid data throughout the course of the study. This may also include, but is not limited to, investigation of unexpected results, incurred sample reanalysis, and analysis for method transfer and comparability. Refer to the applicable supplemental laboratory manuals for detailed collection and handling procedures.

### 7.1 Schedule of Assessments

**Table 1. Schedule of Assessments**

	30-day Screening	Open-Label Run-in Period h				Double Blind Treatment Period g						Follow-Up
Weeks		Run-in Visit 1	Run-in visit 2	Run-in visit 3	Run-in ET	0 g	12	24	36	48/ET	Disease Assessment e	Safety (EOS) i
Days	-198 (from Day 1)	-168 (from Day 1)	-84 (from Day 1)	-7 (from Day 1)		Day 1						30
GENERAL & SAFETY ASSESSMENTS												
Informed consent	X											
Part 1 Eligibility Criteria	X											
Part 2 Eligibility Criteria		X	X	X		X						
Medical/Medication history	X											
Concomitant medications		X	X	X	X	X	X	X	X	X	X	
Adverse events		X	X	X	X	X	X	X	X	X	X	
Serious adverse events	X	X	X	X	X	X	X	X	X	X	X	X
Physical examination a	X	X	X	X	X	X	X	X	X	X	X	
Vital signs	X	X	X	X	X	X	X	X	X	X	X	
Weight	X					X				X		
Height	X											
LABORATORY ASSESSMENTS												
Pregnancy test (serum) b	X											
Pregnancy test (urine) b, c		X				X	X	X	X	X		
Tuberculosis testing d	X											
Hematology and chemistry profile	X		X	X				X		X	X	
Rheumatoid Factor and anti CCP antibody						X						
Hepatitis B surface antigen/core antibody & hepatitis C virus antibody j	X											
Erythrocyte Sedimentation Rate	X	X	X	X		X	X	X	X	X	X	
C-reactive Protein	X	X	X	X		X	X	X	X	X	X	
Urinalysis	X			X								
Blood for biomarker analysis						X		X		X		

Footnotes defined on the next page of the table

